2.8 Subgroups for Analysis

There are no planned subgroup analyses for this trial.

2.9 Handling of Missing Data

The purpose of this trial is to validate an algorithm by comparing measurements using two methods. In order to evaluate the primary endpoint, a physical measurement must be recorded from each method, and thus, there is no planned sensitivity analysis or imputation procedure for missing data.

2.10 Poolability

This trial is designed to be conducted in up to 15 centers in the United States. Given the sample size allocated for the primary endpoint, individual centers may not have adequate sample to assess individual center effect. Therefore, no formal poolability analysis is planned with overall results deemed poolable for interpretation of the study endpoints.

2.11 Multiplicity

This study includes a single primary endpoint. Thus, no Type I error adjustment is necessary.

Statistical Analysis Plan

2.12 Adjustments for Covariates

Unless otherwise specified, no adjustments for covariates will be made for any of the variables in the analyses.

3.0 DESCRIPTIVE ENDPOINTS AND ADDITIONAL DATA

3.1 Baseline and Demographic Characteristics

The following baseline and demographic variables will be summarized for the subjects in the Enrolled population: gender, age, ethnicity, race, cardiac disease history, medical history and co-morbidities, vital signs, and laboratory assessments.

3.2 Adverse Events

Adverse events are defined in Section 7.1 of the Clinical Investigational Plan. All adverse events will be summarized for all subjects in the Enrolled population as number and percentage of all subjects who experience the event and the total number of events.

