5.2 Subject Recruitment/Screening and Informed Consent

5.2.1 Subject Recruitment and Screening

The following assessments are performed as part of the subject recruitment process prior to obtaining informed consent:

• Confirmation of prior CardioMEMS PA Sensor implantation.

A member of the site's clinical investigation team previously trained to the CIP must evaluate patients for the general clinical investigation eligibility criteria, and if applicable, will enter the patients into a site-specific recruitment/screening log. A patient who does not satisfy all general eligibility criteria prior to informed consent is considered a recruitment failure and should not be enrolled in the clinical investigation.

Sites will ask patients meeting general inclusion criteria and no general exclusion criteria to sign an Informed Consent form following the established Informed Consent process (described in Section 5.2.2) if they wish to participate in the clinical investigation. Sites will enter these patients into the recruitment/screening log. Once a duly dated and signed Informed Consent form is obtained, sites will confirm patients meet all eligibility criteria.

Only subjects who meet all inclusion and no exclusion criteria and have consented to the study are considered enrolled in the study. All other subjects should be considered screen failures. The Principal Investigator or the delegated clinical investigation personnel will record the screen failure in the hospital records and on a recruitment/screening log as required.

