5.3.2 Inclusion Criteria

- 1. Subject is willing and able to provide written informed consent prior to any clinical investigation-related procedure.
- 2. Subject is implanted with the CardioMEMS PA Sensor for a minimum of 3 months at time of consent.
- 3. Subject is ≥ 18 years of age.
- 4. Subject is willing and able to undergo several cardiac MRI scans. This is including but not limited to:
 - Subject must have all MRI compatible devices
 - Subject must be able to hold their breath during imaging
 - Subject must be free of all metal bodies, fragments, or implants that would prohibit MRI imaging
- 5. Subject is willing and able to upload PA pressure information (i.e., take daily CardioMEMS readings and have their hemodynamic information collected at study visits) and comply with the follow-up requirements.

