5.3.3 Exclusion Criteria

- 1. Subject will receive or is likely to receive an advanced therapy (e.g., mechanical circulatory support or cardiac transplant) in the next 6 months.
- 2. Subject was implanted with Cardiac Resynchronization Therapy (CRT)-Pacemaker (CRT-P) or CRT-Defibrillator (CRT-D) for less than 90 days prior to consent.
- 3. Subject is pregnant or planning to become pregnant in the next 6 months.
- 4. Subject is enrolled into another trial with an active treatment arm.
- 5. Subject has significant congenital heart disease that has not been repaired.
- 6. Subject is implanted with mechanical right heart valve(s).
- 7. Subject has unrepaired severe valvular disease.
- 8. Subject has an anticipated life expectancy of < 6 months.
- 9. Subject has an active, ongoing infection, defined as being febrile, an elevated white blood cell count, on intravenous antibiotics, and/or positive cultures (blood, sputum, or urine).
- 10. Subject has had a major cardiovascular event (e.g., unstable angina, myocardial infarction, percutaneous coronary intervention, open heart surgery, or stroke, etc.) within 90 days prior to consent.
- 11. Subject has any condition that, in the opinion of the Investigator, would not allow for utilization of the CardioMEMS HF System to manage the subject using information gained from hemodynamic measurements to adjust medications, including the presence of unexpectedly severe pulmonary hypertension (e.g., trans-pulmonary gradient >15) at implant RHC, a history of non-compliance, or any condition that would preclude ability to obtain CardioMEMS PA Sensor readings and paired cardiac MRI data from being collected.
- 12. Subjects who, in the opinion of the investigator, are at-risk for serious adverse reaction to Dobutamine (ex. subjects with idiopathic hypertrophic subaortic stenosis and subjects who have shown previous manifestations of hypersensitivity to Dobutamine) should be excluded from the study.

Sites should instruct female patients of childbearing potential to use safe contraception (e.g., hormonal contraceptives: contraceptive pills, implants, transdermal patches hormonal vaginal devices, injections with prolonged release.) It is accepted, in certain cases, to include subjects having a sterilized regular

Template: 86357 Rev. J Page **18** of **61**

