5.4 Subject Enrollment

A patient is considered enrolled in the clinical investigation only when they have met all inclusion and no exclusion criteria and have provided written informed consent. If subjects enter the study without meeting all the items listed above, they should complete all follow-up requirements. These subjects are considered CIP deviations.

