2.0 ANALYSIS CONSIDERATIONS

2.1 Analysis Populations

2.1.1 Enrolled Population

The Enrolled population includes all enrolled subjects (development phase and validation phase),

- Informed Consent obtained
- Inclusion/Exclusion criteria satisfied

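### On the visible text, the adverse event summary leaves out ineligible subjects whom the protocol keeps in follow-up

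*SAP*

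**What the plan says.** - **AE summary.** SAP 3.2: "All adverse events will be summarized for all subjects in the Enrolled population". It reports the number and percentage of subjects with each event and the total number of events. No safety, as-treated or all-consented population is visible in either document.
- **Population.** SAP 2.1.1 and protocol 8.1.1 each list two conditions for the Enrolled population: consent obtained, and "Inclusion/Exclusion criteria satisfied". In both places the introductory sentence stops at a comma, so some wording is not visible.
- **Meaning of enrolled.** Protocol 5.4: "A patient is considered enrolled in the clinical investigation only when they have met all inclusion and no exclusion criteria", together with written consent. Protocol 5.2.1 opens its definition with "Only subjects who meet all inclusion and no exclusion criteria", and protocol 6.1 repeats the restriction.
- **Ineligible entrants.** Protocol 5.4 continues: "If subjects enter the study without meeting all the items listed above, they should complete all follow-up requirements". It classes them as deviations from the investigation plan.
- **Exposure.** Protocol 3.0 gives each subject cMRI at both visits. Protocol 15.3 has a study medication given at both visits, and SAP 1.4.2 lists dobutamine measurements at both.

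**The concern.** The protocol foresees a group that enters without meeting the criteria and stays to the end, while the SAP ties its AE summary to a population defined by meeting them. A programmer who applies the written definition would drop these subjects from both the numerator and the denominator of the AE table.

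Some criteria screen for risk from the study's own procedures. Exclusion 12 covers "Subjects who, in the opinion of the investigator, are at-risk for serious adverse reaction to Dobutamine". Inclusion 4 requires, among other things, "Subject must be free of all metal bodies, fragments, or implants that would prohibit MRI imaging". A subject retained despite failing one of these is someone whose AEs a safety summary should count. The study runs under an IDE and is meant to support market approval, so the AE summary should cover everyone who had the study procedures.

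**Working it through.** The documents give no figure on this point, so there is nothing to reproduce. The check is which subjects each rule admits.

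**Step 1. Follow an ineligible entrant through the text.**

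| Place | Treatment of a subject who entered without meeting the criteria |
|---|---|
| Protocol 5.4, first sentence | Not enrolled |
| Protocol 5.4, following sentences | Completes follow-up; counted as a deviation |
| SAP 2.1.1 and protocol 8.1.1 | Fails the second listed condition of the Enrolled population |
| SAP 3.2 | Not in the AE summary |
| SAP 3.3 | Early terminations, including deaths, by analysis population; the one visible population has the same restriction |
| SAP 3.4 | The deviation is counted, but not the subject's AEs |

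**Step 2. Does the result depend on the truncated sentence?** Only partly. Even without the two listed conditions, the Enrolled population consists of enrolled subjects, and protocol 5.2.1, 5.4 and 6.1 each make eligibility part of being enrolled. A hidden exception is possible, but it would then have to be reconciled with those three sections.

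**Step 3. Scale, as illustration only.** Protocol Appendix VII caps enrolment at 90. On the literal reading, ineligible entrants are not enrolled, so they come on top: assume 90 enrolled plus k ineligible entrants. Both k and the relative risk RR of an event in them are assumptions.

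For an event type seen in exactly one subject, the chance that this subject is outside the table is RR·k / (RR·k + 90).

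| | k = 1 | k = 5 |
|---|---|---|
| RR = 1 | 1/91 = 1.1% | 5/95 = 5.3% |
| RR = 5 | 5/95 = 5.3% | 25/115 = 21.7% |

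- With k = 0 there is no effect.
- If k = 1 and the single event is in that subject, the table shows 0/90 instead of 1/91 = 1.1%. The exact (Clopper-Pearson) two-sided 95% upper limit is 1 − 0.025^(1/90) = 4.0% for 0/90. For 1/91 it is the 97.5% point of a Beta(2, 90) distribution, 6.0%.
- If k = 1, that subject has no event and 5 enrolled subjects do, the table shows 5/90 = 5.56% instead of 5/91 = 5.49%, which is negligible.

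So the omission matters only for a rare event that happens to fall in a retained ineligible subject.

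**The case against.** The strongest reply is that the definition cannot be read in full, and that the listed conditions may describe steps confirmed at entry and not a later filter. Protocol 5.4 deals with these subjects under the enrolment heading, says they enter the study, and labels them deviations. That is how a participant entered in error is normally handled, and the sponsor may well count them. This stands as a reason for caution: the text supports an exclusion when applied literally, but does not show that one is intended. It does not remove the point, because protocol 5.4 itself restricts enrolment to eligible subjects and nothing visible brings the others back into the AE summary.

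It is also fair that the plan tries to keep the number small. Eligibility is confirmed after consent (protocol 5.2.1 and 6.1), the sponsor grants no waivers (protocol 10.5), and the deviations are summarised (SAP 3.4). The larger figures above need an assumed fivefold risk. Any rule in the imaging and medication sections that withholds procedures from a subject found ineligible cannot be seen.

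A reader might infer more: that AEs in these subjects are not collected at all. Protocol 5.2.1 says "All other subjects should be considered screen failures", and protocol 7.3.1 collects no AEs in screen failures. The documents do not support that inference. In context, those sentences and protocol 6.1.1 concern screening. Protocol 5.4 gives retained subjects a different label, and protocol 11.4 and 15.5 favour collection. The gap is in tabulation.

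**Conclusion.** The point holds as a minor one. On the visible text, and applied literally, the only visible AE summary omits subjects whom protocol 5.4 keeps in follow-up despite unmet criteria. This assumes that the truncated definition hides no exception.

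The number of such subjects is unknown and may be zero. Only the descriptive AE table is affected. A reader might infer that the validation result or safety oversight is compromised, but nothing here supports that: the primary endpoint, the success criterion in SAP 2.7 and the individual reporting of SAEs do not depend on this table.

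**What to change.** In SAP 3.2, with a matching line in SAP 2.1, summarise AEs in the Enrolled population plus every consented subject who was retained under protocol 5.4, or in whom any baseline or 3-month study-visit procedure (cMRI, study medication or CardioMEMS study reading) was started, regardless of eligibility.

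State that screen failures who had screening tests only are not included. Protocol 5.3.1 places non-standard screening tests after consent, and protocol 7.3.1 collects no AEs in screen failures. A looser rule based on any procedure could therefore add subjects without AE data to the denominator and dilute the percentages.

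The cost is about one sentence in the SAP, and nothing changes if no such subject exists. The AE denominator may differ slightly from that of the baseline table in SAP 3.1, which a footnote can explain, and the AE rates may look slightly less favourable.

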3.3 Subject Early Termination

Subject early termination reasons including deaths, withdrawals, lost-to-follow-up, etc. will be summarized by analysis population at all scheduled visits.

3.4 Protocol Deviation

[figure not shown]
Protocol deviations will be summarized by major and minor categories for subjects in whom a protocol deviation was reported.

3.5 Descriptive Endpoints or Additional Data

Descriptive endpoints will evaluate data for the following data samples:

- 1) Baseline measurements recorded at rest
- 2) Baseline measurements recorded following introduction of Dobutamine
- 3) All Baseline measurements
- 4) 3 Month measurements recorded at rest
- 5) 3 Month measurements recorded following introduction of Dobutamine
- 6) All 3 Month measurements
- 7) Baseline and 3 Month measurements recorded at rest
- 8) Baseline and 3 Month measurements recorded following introduction of Dobutamine
- 9) All Baseline and 3 Month measurements

Statistical Analysis Plan

4.0 **DOCUMENTATION AND OHER CONSIDERATIONS**

7.0 APPENDICES

[figure not shown]
Statistical Analysis Plan

APPENDIX B: SAMPLE SIZE CALCULATION DETAILS

86379 Ver. G Template

[figure not shown]

Statistical Analysis Plan

APPENDIX D: STATISTICAL ANALYSIS PLAN REVISIONS

86379 Ver. G Template

Ver	Details	Rationale
